Cover Page

Official Title :

Evaluation of a Contextual, Behavioral, and Cognitive-Based Program to Improve Ophthalmic Compliance in Children and Adolescents with Special Needs

NCT Number :

NCT06717282

Study Type: Interventional (Single-arm, Pre–Post)

Version: Final

Date: 2026-01-19

Study Protocol and Statistical Analysis Plan

1. Background and Rationale

Children and adolescents with special needs, including autism spectrum disorder, developmental delay, and intellectual disability, present a significantly higher prevalence of visual problems compared with typically developing peers. Early ophthalmic assessment and regular follow-up are essential; however, cooperation during ophthalmic examinations remains a major barrier. Sensory hypersensitivity, motor limitations, attentional difficulties, and cognitive challenges frequently prevent completion of standard ophthalmic assessments.

Clinical experience and prior evidence suggest that structured interventions integrating contextual familiarization, behavioral reinforcement, and task-oriented cognitive support may improve cooperation during ophthalmic examinations and enhance participants' ability to complete examinations that require higher levels of cognitive engagement.

This study therefore evaluates a contextual, behavioral, and cognitive-based ophthalmic adaptation program designed to enhance ophthalmic compliance in children and adolescents with special needs.

2. Study Objectives

To evaluate the effectiveness of a contextual, behavioral, and cognitive-based ophthalmic adaptation program in improving cooperation during ophthalmic examinations and visual functional performance following the intervention.

3. Study Design

This study is a single-arm, pre-post interventional clinical trial. All eligible participants receive the intervention. Outcomes are assessed before and after completion of the intervention. Participants with complete pre- and post-intervention data are included in the final analysis.

4. Study Setting

Recruitment and assessments are conducted at the Vision Center for People with Special Needs, National Taiwan University Hospital.

5. Participants

Inclusion Criteria

Participants must meet all the following criteria:

- (1) Aged 2 to 18 years.
- (2) Diagnosed with or suspected of autism spectrum disorder, developmental delay, or intellectual disability.
- (3) Demonstrated difficulty cooperating with routine ophthalmic examinations in general ophthalmology settings due to cognitive, behavioral, or emotional factors.

Exclusion Criteria

Participants will be excluded if they meet the following criterion:

- Children or adolescents with developmental delays or disabilities who can complete routine ophthalmic examinations or standard vision screenings during regular ophthalmology visits or school-based health screenings without specialized support.

6. Sample Size and Analysis Population

A total of 20 participants are enrolled. Participants with complete pre- and post-intervention outcome data are included in the final statistical analysis.

7. Study Procedures

Baseline Assessment

Before intervention, participants undergo assessment using:

- (1) Visual Function Battery for Children with Special Needs (VFB-CSN)
- (2) Near Detection Scale (NDS)
- (3) Functional Vision Questionnaire (FVQ)
- (4) Ophthalmic Compliance and Adaptation Questionnaire
- (5) Parent-reported measures (Vineland Adaptive Behavior Scales–III, CASD-C, Sensory Profile, HVFQI)

Intervention

Participants receive six individual one-hour sessions, typically once every two weeks, delivered by occupational therapists specialized in visual rehabilitation. Intervention components include:

- (1) Contextual strategies (environmental familiarization)
- (2) Behavioral strategies (positive reinforcement)
- (3) Cognitive strategies (visual supports and structured instruction)

Post-intervention Assessment

All baseline outcome measures are re-administered following completion of the intervention.

8. Outcome Measures

Primary Outcome

Change in overall visual functional performance (VFB-CSN).

Secondary Outcomes

Change in ophthalmic examination compliance as measured by the Ophthalmic Compliance and Adaptation Questionnaire.

9. Statistical Considerations

9.1 Analysis Population

The analysis population includes participants who completed both pre-intervention and post-

intervention assessments. Participants with incomplete outcome data were excluded from the final statistical analysis.

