9.4 Inferential Statistical Analysis

Given the small sample size and the expected non-normal distribution of outcome measures, non-parametric statistical tests are used to compare pre-intervention and post-intervention outcomes.

Comparisons between pre- and post-intervention scores for the primary and secondary outcomes are conducted using appropriate non-parametric methods for paired data.

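### Only a completers analysis is described, and its rule drops whole participants: a selection-bias risk of unknown size and direction, and possible loss of usable VFB-CSN pairs

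*Combined protocol and SAP*

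**What the plan says.** Three places in the combined protocol and SAP define who is analysed.

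- Section 3: "Participants with complete pre- and post-intervention data are included in the final analysis".
- Section 6: "A total of 20 participants are enrolled", followed by "Participants with complete pre- and post-intervention outcome data are included in the final statistical analysis".
- Section 9.1 defines the population by completion of the assessments at both times, then adds: "Participants with incomplete outcome data were excluded from the final statistical analysis".

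The requirement is thus worded as data, as outcome data, and as assessments. Section 9.4 adds only that the comparisons are "conducted using appropriate non-parametric methods for paired data", with no test named. Section 7 lists eight instruments at baseline and adds: "All baseline outcome measures are re-administered following completion of the intervention". Sections 8 and 9.2 name two outcomes, the VFB-CSN (primary) and the compliance questionnaire (secondary).

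The available text contains no analysis of all enrolled children, no imputation or sensitivity analysis, no comparison of completers with non-completers, no expected or observed number of incomplete cases, and no plan to report reasons. Section numbering goes from 9.5 to 9.7, so these statements apply only to the text supplied.

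**The concern.** There are two separate problems.

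**Selection.** Section 1 says of this population that "cognitive challenges frequently prevent completion of standard ophthalmic assessments", and expects programs of this kind to raise the "ability to complete examinations that require higher levels of cognitive engagement". Difficulty cooperating with routine examinations is an entry criterion (Section 5). If ability to complete is part of what the program is meant to change, having a complete post-intervention record may be related to response. A single-arm change computed in completers then describes completers and not the 20 enrolled, and there is no control arm in which similar loss could be seen. A reader can get the number left out by subtracting the analysed n from 20. The reasons, the timing and the likely effect on the result cannot be recovered from anything the available text plans to report.

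**Unit of exclusion.** Section 9.1 excludes participants, not outcome pairs. A child with both VFB-CSN scores but a missing compliance form has incomplete outcome data and, as worded, leaves the primary analysis too. If outcome data is read in the light of Section 7, where all eight instruments count as baseline outcome measures, any one missing parent form could have the same effect.

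**Working it through.** The plan gives no figure for missing data and no power, SD or dropout rate behind the 20, so there is nothing of its own to reproduce. From the documents: N = 20, paired design, two-sided tests at 0.05 (Sections 6, 9.4, 9.5). Assumed: the number missing m, the link between loss and change, and the sign test without ties, because no test is named.

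**1. Size of the bias in general.** With mean change C in completers and E in those excluded:

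C − [(20 − m)C + mE]/20 = (m/20)(C − E)

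If C and E differ by 1 SD of change, this is 0 at m = 0, 0.05 SD at m = 1, 0.10 SD at m = 2 and 0.20 SD at m = 4. The sign is that of C − E, which the documents do not give.

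**2. Bounds on the proportion improved.** Exact two-sided sign test, p = 2 × P(X ≥ r) with X ~ Binomial(n, 0.5), and exact 95% CI for the all-20 proportion at the bounds:

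| Completers improved | p | Missing counted as not improved | Missing counted as improved |
|---|---|---|---|
| 14/18 (m = 2) | 2 × 4048/262144 = 0.031 | 14/20 = 70% (CI 46% to 88%), p = 2 × 60460/1048576 = 0.115 | 16/20 = 80% (CI 56% to 94%), p = 2 × 6196/1048576 = 0.012 |
| 15/18 (m = 2) | 2 × 988/262144 = 0.008 | 15/20 = 75%, p = 2 × 21700/1048576 = 0.041 | not needed |
| 15/19 (m = 1) | 2 × 5036/524288 = 0.019 | 15/20 = 75%, p = 0.041 | 16/20 = 80%, p = 0.012 |

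14/18 is the smallest significant count at n = 18, so it is the case most easily overturned. The other two rows hold.

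**3. Effect on false findings of improvement.** Simulation with no true change, normal change scores (illustrative only, since Section 9.4 expects non-normal data), 200,000 trials per setting and exact signed-rank critical values on the remaining n. Children are removed in order of a propensity correlated with poor change; the nominal rate is 2.5% in the direction of improvement.

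| Correlation | 2 lost: rate, bias | 3 lost: rate, bias |
|---|---|---|
| 0 | 2.4%, 0 SD | 2.2%, 0 SD |
| 0.3 | 4.0%, 0.06 SD | 4.4%, 0.08 SD |
| 0.5 | 5.8%, 0.09 SD | 7.1%, 0.13 SD |

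Repeat runs agreed to within 0.2 percentage points.

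**4. Direction.** With a true change of 0.7 SD and 3 children lost because they did well, the estimate falls to 0.62 SD at correlation 0.3 and 0.57 SD at 0.5. If loss is linked instead to low baseline (correlation 0.5, 3 lost), the bias is −0.05 SD when low-baseline children gain more (baseline-change correlation −0.4), 0 when the two are unrelated, and +0.05 SD when they gain less (+0.4). Even knowing that the least cooperative children were lost would not fix the sign.

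**The case against.** The strongest case against is that no bias is shown. The documents give no dropout count, mechanism or correlation. A trait shared by every enrolled child does not by itself cause selective loss. The barrier in Section 1 concerns standard assessments and the one in Section 5 routine examinations in general settings, whereas the study assesses children in a dedicated vision centre (Section 4) with a battery named for this population. The link to VFB-CSN completion is plausible, not demonstrated. The exclusion rule is stated openly, paired tests need pairs, Section 9.3 already plans baseline summaries that are not expressly limited to completers, and with one child lost even the weakest significant sign-test result survives. All of this stands. It limits the point to a risk, but it does not supply the missing reporting or repair the participant-level rule.

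Three stronger readings are tempting and unsupported:

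- A reader might infer that the completers result is inflated. The outcome is a change, and step 4 shows the error can go either way.
- A reader might infer from the past tense in Section 9.1 that children have already been removed. The text gives no count, and Section 12 places approval before data analysis.
- A reader might infer that requiring all eight instruments at both times would gut the sample: at 95% completion per administration, 20 × 0.95^16 = 8.8 children. That is an extreme. It assumes independent missingness over 16 administrations, and forms given in one visit tend to be missing together. Sections 8 and 9.2 also allow the narrower reading of two outcomes.

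The proposed bounds can be criticised too: they apply to the proportion improved, not to the planned VFB-CSN comparison. That is right and must be stated with them.

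**Conclusion.** The point holds as a risk and as a wording defect, not as a demonstrated bias. The available text describes one analysis, in completers only, and removes participants rather than pairs; a section between 9.5 and 9.7, if one exists, could change this. The size and direction of any selection bias are unknown, and it is zero if all 20 complete or if loss is unrelated to change. Under the assumed losses of two or three children and correlations up to 0.5, bias under no true change reaches about 0.13 SD and the false-improvement rate about 7% against a nominal 2.5%. Two missing children are enough to move a borderline result across 0.05 in the worst case, but not a somewhat stronger one. The possible loss of a usable VFB-CSN pair through a gap in another measure follows from the wording of Section 9.1 and needs no assumption about mechanism.

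**What to change.** Amend Section 9.1 and align Sections 3 and 6.

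1. Judge completeness separately for each outcome, so that a VFB-CSN pair or a compliance pair is never dropped because another form is missing.
2. Keep the completers comparison and add one labelled, supportive sensitivity analysis of all 20 enrolled: the proportion improved (post better than pre, ties counted as not improved) with an exact 95% CI, counting missing children first as not improved and then as improved. State that these are limits rather than estimates, that they bound this proportion and not the VFB-CSN change, and that counting ties as not improved puts the no-effect proportion below 50%. The proportion is not a new endpoint.
3. Report the number, timing and reasons for exclusions, compare baseline data of completers and non-completers, and limit conclusions from the completers result to completers.

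If exclusions are already known, say so and date the addition. If a Section 9.6 exists, check it first.

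The cost is SAP wording and a small analysis of data already held; sample size, outcomes and procedures do not change. The downside is that the bounds may be wide and the result less favourable. If nobody is lost, the sensitivity analysis adds nothing to the completers analysis, and one sentence saying so is enough.

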9.2 Outcome Measures

Primary Outcome

Change in overall visual functional performance and subscale scores as measured by the Visual Function Battery for Children with Special Needs (VFB-CSN).

Secondary Outcome

Change in ophthalmic examination compliance as measured by the Ophthalmic Compliance and Adaptation Questionnaire.

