9.5 Significance Level

All statistical tests are two-tailed. Statistical significance is defined as a p-value of less than 0.05.

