9.7 Statistical Software

All statistical analyses are performed using standard statistical software (e.g., SPSS).

10. Ethics and Human Subjects Protection

This study was reviewed and approved by the Institutional Review Board. Written informed consent was obtained from caregivers prior to participation.

11. Data Management and Confidentiality

All data are de-identified and securely stored. Access is restricted to authorized research personnel.

12. Consistency Statement

This protocol represents the final version reviewed and approved prior to data analysis. All analyses are conducted in accordance with the predefined Statistical Analysis Plan.

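### Sections 8 and 9.2 define the primary outcome differently (overall VFB-CSN alone, or overall plus subscales), and the plan does not say which score decides the trial

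*Combined protocol and SAP*

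**What the plan says.** - **Section 2** sets the objective as effectiveness "in improving cooperation during ophthalmic examinations and visual functional performance following the intervention".
- **Section 8**, under the primary outcome: "Change in overall visual functional performance (VFB-CSN". Subscales are not mentioned.
- **Section 9.2**, under the same heading: "Change in overall visual functional performance and subscale scores", measured by the same battery. The subscales are neither listed nor counted.
- **Sections 8 and 9.2** agree on the secondary outcome: "Change in ophthalmic examination compliance as measured by the Ophthalmic Compliance and Adaptation Questionnaire".
- **Section 9.4**: "Comparisons between pre- and post-intervention scores for the primary and secondary outcomes are conducted using appropriate non-parametric methods for paired data".
- **Section 9.5**: "All statistical tests are two-tailed. Statistical significance is defined as a p-value of less than 0.05".
- The next heading after 9.5 is "9.7 Statistical Software", so the supplied text has no Section 9.6.
- **Section 6** enrols 20 participants. **Section 9.1** adds: "Participants with incomplete outcome data were excluded from the final statistical analysis". The number analysed may therefore be below 20.
- **Section 12** describes the document as final before data analysis and says that the analyses follow the SAP.

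**The concern.** Section 8 describes one endpoint; Section 9.2 describes a family of endpoints of unstated size. Both are current text in the same final version. A reader cannot tell from them which test answers the primary question, or whether one, some or all of the scores must reach significance.

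The objective is improvement. If any one score is enough, the trial could report improved visual function on the strength of a single subscale while the overall score had not significantly improved. The 0.05 level in Section 9.5 would then not be the error rate of that claim. The study has 20 participants and no control group, so its main claim rests on the pre-specified pre-post test. Which test that is should not be open to choice once results are known.

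**Working it through.** **Side-by-side reading.** Both sections make the overall VFB-CSN result primary. They differ on whether the subscales are primary too. Section 9.4 refers to the outcomes as a group, and Section 9.5 gives each test the same threshold. Section 12 points to the SAP, and so to the wider wording of 9.2, but it names no deciding score and no order.

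**The plan's own figure.** With one primary test the error rate is 1 − 0.95 = 0.05, as in Section 9.5. For an exact signed-rank test with n = 20, the ranks sum to 20 × 21 / 2 = 210. The two-sided test rejects when the smaller rank sum is 52 or less, with exact level 0.0484, or 0.0242 in each direction. That is the Section 8 reading, and it has no inflation.

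**Inputs under the any-one-score reading.** From the documents: 20 participants, two-tailed 0.05 for each test, no adjustment. Assumed, because the documents do not give them:
- k = 2, 4, 6 or 8 subscales;
- equal correlation ρ = 0, 0.5, 0.7 or 0.9 between subscale changes;
- overall score equal to the sum of the subscales;
- the Wilcoxon signed-rank test;
- all 20 participants complete.

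**Crude ceiling.** Treating the k + 1 tests as independent gives 1 − 0.95^(k+1) = 0.143, 0.226, 0.302 and 0.370 for k = 2, 4, 6 and 8. This overstates the rate, because the overall score is built from its subscales.

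**Simulation with no true change.** Subscale change = √ρ × shared normal term + √(1−ρ) × own normal term; overall = sum; 100,000 runs per cell.

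Chance that at least one score shows a significant *improvement* (overall score alone: 2.3% to 2.5% in every cell):

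| k | ρ = 0 | 0.5 | 0.7 | 0.9 |
|---|---|---|---|---|
| 2 | 5.9% | 4.8% | 4.3% | 3.7% |
| 4 | 10.4% | 8.0% | 6.7% | 4.9% |
| 6 | 14.6% | 10.5% | 8.6% | 5.7% |
| 8 | 18.7% | 12.8% | 9.8% | 6.3% |

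Chance that at least one score is significant in *either direction* (overall score alone: 4.8%):

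| k | ρ = 0 | 0.5 | 0.7 | 0.9 |
|---|---|---|---|---|
| 2 | 11.5% | 9.9% | 8.8% | 7.3% |
| 4 | 20.1% | 16.1% | 13.4% | 9.8% |
| 6 | 27.8% | 21.1% | 17.0% | 11.3% |
| 8 | 34.5% | 25.5% | 19.9% | 12.6% |

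With k = 4 and ρ = 0.5, 5.6 of the 8.0 percentage points in the first table come from a subscale that improves when the overall score does not significantly improve.

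**Sensitivity of the improvement range.**
- 15 completers: 3.7% to 18.6%.
- Heavy-tailed changes (t, 3 degrees of freedom): 3.7% to 18.5%.
- Tied scores, 38% of subscale changes zero: 3.7% to 18.5%.
- Tied scores, 60% of subscale changes zero: 3.6% to 16.6%.

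**Effect of the remedies** (k = 2, 4, 8; ρ = 0, 0.5, 0.9). With the overall score alone, false improvement is 2.3% to 2.5%. With Holm across the overall and subscale scores it is 0.9% to 2.2%, and 1.7% to 4.4% in either direction.

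**Power cost of making all the scores primary.** Suppose the mean change in the overall score is 0.68 SD, which gives about 80% power at 0.05 with n = 20. At the Bonferroni level 0.05/(k + 1):

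| k | Level | Power for overall score |
|---|---|---|
| overall alone | 0.05 | 80% |
| 2 | 0.0167 | 63% |
| 4 | 0.0100 | 55% |
| 8 | 0.0056 | 45% |

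Holm can only improve on these.

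**The case against.** The conflict is narrow. Both sections make the overall result primary and 9.2 lists it first, so a natural reading is a headline score with its components reported beside it. Nowhere does the plan say that a lone significant subscale makes the trial positive. That is correct, and it is why the inflation figures are conditional. It does not supply the missing rule: under 9.2 the subscales are primary outcomes tested at 0.05, and nothing there ranks them below the overall score.

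The size depends on inputs that the documents do not give, and several improvement rates lie below 5%. This also stands. The like-for-like comparison is 2.4% for improvement and 4.8% for either direction, and every cell exceeds its comparator.

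An unseen Section 9.6 might contain a multiplicity rule. If so, that part of the point falls away, but the mismatch between Sections 8 and 9.2 remains.

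Section 12 arguably makes 9.2 govern, so reverting to Section 8 is a choice. That is fair, and an alternative is offered for that case. It is also fair that the documents neither define a VFB-CSN total nor name the paired test; the amendment should settle both.

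**Conclusion.** The point holds. Two current sections define the primary outcome differently, and nothing in the supplied text says which score decides. That conclusion needs no simulation and is held with high confidence. The absence of a multiplicity rule is less certain, because it depends on there being no Section 9.6.

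The consequence depends on the reading. Under Section 8 there is no inflation. If any one score suffices, a false claim of improvement has a chance of about 4% to 19% instead of 2.4%, and a false positive in either direction about 7% to 34% instead of 4.8%. The range rests on the assumptions listed above and is illustrative, not a bound. Because the ambiguity concerns the test that carries the main claim, it must be corrected.

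**What to change.** **Preferred.** In Section 9.2, remove the subscales from the primary outcome and state that the overall VFB-CSN score, tested at two-sided 0.05, alone decides the primary question, as in Section 8. Say how the overall score is calculated and name the paired test. Keep the compliance questionnaire as the secondary outcome. Place the subscales after it as supportive, with estimates and 95% confidence intervals and no claims of significance. If subscale tests are wanted, use a fixed order that stops at the first non-significant step: overall score, compliance questionnaire, then Holm across the subscales.

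**Alternative, if the sponsor intends the subscales to be primary.** List them, apply Holm across the overall and subscale scores, and change Section 8 to match.

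**In either case** issue a dated amendment that states whether outcome data had been seen and whether a Section 9.6 exists.

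**Cost.** No new data. Under the preferred option a lone significant subscale can no longer be called a primary success. Under the alternative, power for the overall score falls as tabulated above. If outcome data have already been seen, the amendment gives transparency but does not restore pre-specification, and the change must be reported as made after the fact.
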